10.4.1 Tumor Based Biomarkers

Interrogation of immune responses within the tumor microenvironment of sarcomas before and after treatment with epacadostat and PD-1 checkpoint blockade.

For each resected specimen, up to 6 cores of tissue will be obtained for tumor immune correlative studies.

a) Density of immune infiltration and immune checkpoint and kynurenine expression of sarcomas: IHC will be used to assess the number and composition of immune infiltrates in order to define the immune cell subsets present within the tumor before and after exposure to epacadostat and pembrolizumab. PD-L1, PD-1, ID0-1 and kynurenine expression within the tumor before and after exposure to epacadostat and pembrolizumab will also be determined by IHC.

The IHC assays will be performed using but are not limited to the following markers: CD3, CD4, CDS, CD25, CD28 CD45RA, CD68, CD69, CCR?, ID0-1, kynurenine, PD-L1, PD-1, CD137, FOXP3, LAG-3, TIM-3, and ICOS. PD-L1 expression by immunohistochemistry staining of archival tumor specimens will be performed with using a QualTek immunohistochemistry-based assay.

b) Phenotype and function of TIL in human sarcomas:

Multiparameter flow cytometry (MFC) performed on freshly dissociated tumor tissue will be used to characterize the tissue T cell populations. We will study the functional significance of PD-1 expression and ID0-1 expression on T cells isolated from sarcomas. Using intracellular cytokine staining (ICS) and MFC analysis on freshly isolated TIL, we will identify the T cell cytokine profiles in

Memorial Sloan Kettering Cancer Center IRB Number: 17-508 A(S)

Approval date: 07-May-2024

accordance to their immune checkpoint profile (PD-1, LAG-3, TIM-3) and level of IDO-1 expression. A range of cytokines representing key lymphocyte subgroups (e.g., Th1, 2 or 17) such as IL-2, TNF-a, IFN-y IL-17 among other inflammatory mediators will be assessed. Functional T cell markers including granzyme Band perforin as well as activation markers such as CD62L, CD44, CD69 will be also included in our analysis.

- c) Tumor Biopsy gene expression profiling: Fresh tumor biopsy will be examined for RNA gene and protein expression by NanoString technology (nCounter® RNA: Protein, PanCancer Immune Profiling Panel) and/or qRT-PCR to detect expression of immune related genes. This panel includes 770 immune related genes including: 109 genes related to cell surface markers for 24 different immune cell types and populations, 30 genes for commonly studied cancer/testis (CT) antigens, over 500 genes for measuring immune response and 40 reference genes.
- d) Neoantigen analysis: Massively parallel sequencing of the whole exome of the tumor tissue and normal blood will be performed for patients who opt in. Genomic DNA will be captured via solution-based hybrid selection and sequenced on the Illumina HiSeq platform by the Genomics Core at MSKCC. The sequencing data will be aligned by the Bioinformatics Core Tumor, using Somatic Sniper, Somatic Indel Detector and Mutect softwares.
- e) Next generation sequencing for T-cell receptor clonality in tumor-infiltrating lymphocytes (TIL): Samples will be analyzed using highthroughput sequencing of the variable 13-chain of the T cell receptor (TCR) to characterize the expansion and clonality of the T-cell repertoire in Tlls.

10.4.2 Peripheral blood studies

Blood samples will be taken prior to initiation of study therapy and on designated time points post-treatment. These samples will be analyzed for:

a.) Immunophenotyping and Functional Analyses:

- Samples will be analyzed by flow cytometry to study the effects of epacadostat and pembrolizumab on various peripheral blood immune cell subsets including, but not limited to T cell subsets (activated, memory and regulatory T cells).
- To explore whether inhibition of both PD-1 and IDO-1 in combination will restore T cell activation and function, peripheral blood mononuclear cells (PBMCs) will be isolated and cryopreserved. Assays of the functional status of effector T cells will

be performed, including, but not limited to assays for interferon-gamma (IFN-y) and granzyme B. This assay will use a non-specific stimulus including but not limited to anti-CD3 and anti-CD28 and would allow for the comparison of the effect of PD-1 blockade alone on T cell function.

- **b.) Soluble Factors:** Baseline and on-treatment serum levels of chemokines, cytokines and other immune mediators will be assessed by techniques that may include but are not limited to ELISA or multiplex assays. Analytes may include, but are not limited to IFN-y, IL-12, IL-10, soluble MICA, C-reactive protein, soluble PD-1 and soluble PD-L1.
- c.) Next generation sequencing for T-cell receptor clonality in peripheral blood: Samples will be analyzed using highthroughput sequencing of the variable 13-chain of the T cell receptor (TCR) to characterize the expansion and clonality of the T-cell repertoire in peripheral blood mononuclear cells.

Table 4. Exploratory Biomarkers

Biomarker name	Assay	Tissue/Body Fluid Tested and Timing of Assay
Peripheral Blood Cells	 Flow cytometric analyses to evaluate activated (HLA-DR+) and memory (CD45RA-) T cells Flow cytometric analyses to evaluated peripheral blood leucocytes including CD4/CD25/FoxP3, CD4/CD8/CD45RA/CCR7, CD4/CD8/LAG3/PD-1/PD-L1, CD4/CD8/LAG3/PD-1/PD-L1, CD4/CD8/CD137/IDO-1 Functional Status of effector T cells assays for interferon-gamma and granzyme B. T-cell subsets and their activation status (CDS+Teff/Treg ratio and ICOS expression 	Blood (Weeks 1(before treatment), 4, 7, 13, 22 and off-study)
Soluble Factors, Serum	Treatment modulation of serum levels of chemokines, cytokines and other immune mediators by ELISA or other multiplex-based assay methods. Primary analysis includes interferon-gamma and IL-10.	Blood Serum (Weeks 1(before treatment), 4, 7, 13, 22 and off-study)
Characterization of Tumor infiltrating lymphocytes	IHC to assess number and composition of immune infiltrates to define immune cell subsets present within	Tumor biopsy at: Baseline

	tumor before and after exposure to treatment. CD3, CD4, CD8 and FOXP3 will be evaluated. 2. Immune cell phenotyping of freshly isolated TIL to evaluate Treg/Teff ratio (CD8+/FoxP3+ cells) and activations markers (ICOS, PD-1, CD69).	Week 7 Progression (optional)
100- 1, PD-L1 & kynurenine expression by IHC	Qualtek immunohistochemistry- based assay for PD-L1	Tumor biopsy at: Baseline Week 7 Progression (optional)
Tumor Biopsy neoantigen analysis	Fresh frozen tumor biopsy will be utilized for massively parallel whole exome sequencing. Available databases such as SNP effect (http://snpeff.sourceforge.neU will be used to determine which mutations are in coding regions and will affect amino acid sequence. NetMHC and the Immune Epitope Database will be utilized to predict MHC Class I binding and T cell interactions, respectively.	Tumor biopsies at baseline Paired normal peripheral blood mononuclear cells at baseline
T-cell receptor sequencing	Highthroughput sequencing of the variable (3 chain of the T-cell receptor.	Tumor biopsy at: Baseline Week 7 Progression (optional)

Table 5. Study calendar -

	Screening	Cycle 1				2	Cycle 3		Off study		
	Screening	Wk1	Wk2	Wk3	Wk4	Wk5	Wk6	Wk7	Wk8	Wk9	visit ¹
EpacadostatA		Х	X	X	Х	Х	Х	Х	Х	Х	
Pembrolizumab ⁸		Х			Х			Х			
Informed consent	Х										
Pathologic Confirmation at study siteJ	x										
Review of concomitant medications	х	х			х			х			
Review of adverse events		х			х			х			x
Physical exam	Х	Х			Х			Х			Х
Routine laboratory testsc	x	х			х			х			Х
Research blood tests ⁰		х			х			х			Х
Hepatitis B, C and HIV	x										
Pregnancy TestE	Х										Х
ECGF	х								Х		Х
ECHO	х										
CT and/or MRI ⁸	х								х		
Biopsy	Х							Х			

- A. Epacadostat will be administered twice daily, orally, continuously from day 1-21 (inclusive) of each treatment cycle, each treatment cycle consists of 21 days
- B. Pembrolizumab will be administered once at a dose of 200mg, intravenously, on day 1 of cycle **1** and every 3 weeks (±3 days) thereafter
- C. Routine laboratory tests at screening, day 1 of cycle 1 and then prior to every scheduled treatment visit(± 3 days) thereafter. All routine blood samples should be obtained prior to the daily dose epacadostat and/or pembrolizumab. routine laboratory tests include: cbc with differential, PT/INR and a PTT, comprehensive metabolic panel, magnesium and phosphorus, fT4, TSH, T3, lipase and amylase
- D. Research blood samples will be collected at week 1 (before treatment), 4, 7,13, 22 and at the date of the off study visit(± 3 days)

- E. Serum pregnancy test (Female subject of childbearing potential should have a negative serum pregnancy at screening and within 72 hours prior to receiving the first dose of both study drugs and at the off study visit.)
- F. An ECG will be performed at baseline, week 8, every 8 weeks subsequently((± 1 week window) and at the off study visit((± 1 week window)
- G. Standard Imaging studies will be performed at baseline, week 8 and every 8 weeks subsequently (± 1 week window) until 56 weeks, and then every 12 weeks thereafter or as per the discretion of the treating investigator and will include CT of chesUabdomen/pelvis and MRI of the affected area if deemed necessary by the study investigator.
- H. Optional biopsy at progression.
- I. The off study visit will take place 30 days(+/- 7 days) after the last dose of study therapy
- J. Pathologic confirmation of the presence of sarcoma at the study site may take place during or before the screening period.

11.0 TOXICITIES/SIDE EFFECTS

Toxicity will be assessed using the NCI CTCAE (version 4.03). (http://ctep.cancer.gov/protocolDevelopment/electronic applications/ctc.htm).

Patients who have received at least one dose of the epacadostat and/or pembrolizumab are available for the safety assessment. Patients who discontinue the study before receiving their first dose of the study treatments will not be available for safety assessment and should be replaced.

Patients whose treatment is interrupted or permanently discontinued due to an adverse event or clinically significant laboratory value must be followed until resolution or stabilization of the event.

A dose delay >6 weeks from the date of the planned dose (i.e., approximately 9 weeks since the previous dose) may require the patient to be discontinued from the study, with exception of patients who undergo surgery. A dose delay >6 weeks from the date of the planned dose (i.e., approximately 9 weeks since the previous dose) due to the occurrence of an adverse event that is considered related to epacadostat and/or pembrolizumab, the subject should be taken off study treatment.

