5.1.3 Administration of Epacadostat

Epacadostat be taken orally twice daily on a continuous dosing schedule at the recommended phase II dose for epacadostat when administered in combination with pembrolizumab. Epacadostat will be administered as a flat-fixed dose, and not by body weight or body surface area. Patients will be provided with a 3 week supply of epacadostat for self-administration at home until at least their next scheduled study visit. Patients will be instructed to return unused study drug to the site at each visit. A study medication diary will be completed by the patients for each dose of epacadostat.

Epacadostat will be taken twice daily orally without regard to food morning and evening, approximately 12 hours apart. There is no priority to the order of administration of epacadostat and pembrolizumab when given in combination; however, th dose of epacadostat should be taken as close to the regularly scheduled 12-hour dosing interval as possible. Patients will be instructed not to chew or crush tablets of study drug. If a patient vomits at any time after dosing, the dose of study drug should not be readministered. Doses of study drug omitted for AEs or any other reason should not be made up later in the day, or at the end of the dosing period. If a dose of epacadostat is missed, the subject should take it as soon as possible within 4 hours of the missed dose. If 4 hours passes, the subject should skip the missed dose and take the next dose as scheduled. All missed doses and schedule deviations should be recorded in the pill diary. Doses of epacadostat will be self-administered except on the days scheduled to be given at the time of a study visit.

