5.2.3 Administration of Pembrolizumab

Pembrolizumab must be prepared and administered by a qualified healthcare professional.

Pembrolizumab at a dose of 200 mg will be administered intravenously on Week 1 of treatment cycle 1 and every 3 weeks (±3 days) thereafter.

Pembrolizumab infusion will be administered as a 30-minute intravenous infusion. Investigators should make every effort to target infusion timing to be as close to 30 minutes as possible. However, given the variability of infusion pumps from site to site, a window of -5 and +10 minutes is permitted (i.e., infusion time is 30 minutes: -5 min/+ 10 min). A central catheter is not required for infusion; however if a subject has a central venous catheter in place, it is recommended that it be used for the infusion. A 0.2 or 0.22 μ m in-line filter made of polyethersulfone (PES) must be used during administration to remove any adventitious particles. If the infusion set does not contain a 0.2 or 0.22 μ m in-line filter, it is recommended to use an extension line containing the filter.

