Note: Exception to be treated to similar Grade 1 toxicity: -G2 alopecia	2	Consider holding for persistent symptoms	Toxicity resolves to ::;; grade 1 or baseline	Restart at same dose	Toxicity does not resolve within 12 weeks of last dose of treatment
-G2 fatigue	nyestigator agre	ement subjects	Toxicity resolves to ::;; grade 1 or baseline. Subjects with AEs that stabilize at grade 2 (such as neuropathy) may resume treatment upon principal investigator approval. Permanent discontinuation of epacadostat in setting of grade 4 toxicities with the exception of grade 4 laboratory abnormalities that are deemed clinically insignificant	Restart at 1 dose level lower	Toxicity does not resolve within 12 weeks of last dose of treatment. Permanent discontinuation should be considered for any severe or life threatening event.

With principal investigator agreement, subjects with a laboratory AE still at grade 2 after 12 weeks may continue treatment in the study only if asymptomatic and controlled.

Adverse events of a potential immunologic etiology or immune-related AEs (irAEs) may be defined as an AE of unknown etiology, associated with drug exposure and consistent with an immune phenomenon. Immune-related AEs may be predicted based on the nature of the compounds, their mechanism of action, and reported experience with immunotherapies that have a similar mechanism of action. Special attention should be paid to AEs that may

be suggestive of potential irAEs. An irAE can occur shortly after the first dose or several months after the last dose of treatment.

If an irAE is suspected, efforts should be made to rule out neoplastic, infectious, metabolic, toxin, or other etiologic causes prior to labeling an AE as an irAE.

Immune-related adverse events may be attributable to epacadostat alone, pembrolizumab alone, or the combination of both agents. If the event is clearly related to one of the agents, follow the instructions specific for that agent. If the event is related to both agents, follow the action taken instructions for both.

Suggested supportive care measures for the management of adverse events with potential immunologic etiology are outlined in Table 16. below. Note that several courses of steroid tapering may be necessary as symptoms may worsen when the steroid dose is decreased.

It may be necessary to perform conditional procedures such as bronchoscopy, endoscopy, or skin photography as part of evaluation of the event.

 Table 16:

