Immune-related AEs	Toxicity Grade or Conditions (CTCAEv4.0)	Study Medication	Action Taken with Study Medication	irAE Management with Corticosteroid and/or Other Therapies	Monitor and Follow-up
			1 dose level. Not Related: Same dose level.		• If Grade 4 lipase/amylase elevation is asymptomatic and abdominal imaging suggests no pathology, study drug administration dosing may continue with medical monitor approval.
		Pembrolizuma b	Withhold until Grade 0- 1	Based on severity of AE administer corticosteroid	Ensure adequate evaluation to confirm
	Immune-related		Withhold until Grade 0-1	s	etiology or exclude other causes
All Other Immune-related AEs		Epacadostat	Related: Reduce by 1 dose level.		
		Not Related: Same dose level.			
	Grade 4 or recurrent	Pembrolizuma b	Permanent! y discontinue		
	Grade 3	Epacadostat	Permanent! y discontinue		

				irAE	
Immuno volotod	Toxicity Grade or	Cturdu	Action Taken with	Management	Manitarand
Immune-related	Grade or	Study	i aken with	with	Monitor and
AEs	Conditions	Medication	Study	Corticosteroid	Follow-up
	(CTCAEv4.0)		Medication	and/or Other	
	,			Therapies	

General Instructions:

- 1. Corticosteroid taper should be initiated upon AE improving to Grade 1 or less and continue to taper over at least 4 weeks.
- 2. For situations where pembrolizumab and epacadostat have been withheld, pembrolizumab and epacadostat/placebo can be resumed after AE has been reduced to Grade 1 or O and corticosteroid has been tapered. Pembrolizumab and epacadostat/placebo should be permanently discontinued if AE does not resolve within 12 weeks of last dose or corticosteroids cannot be reduced to:S 10 mg prednisone or equivalent per day within 12 weeks.
- 3. For severe and life-threatening irAEs, IV corticosteroid should be initiated first followed by oral steroid. Other immunosuppressive treatment should be initiated ifirAEs cannot be controlled by corticosteroids.
- 4. Pembrolizumab should be permanently discontinued if Stevens Johnson Syndrome (SJS) or Toxic Epidermal Necrolysis (TEN) occurs.

NOTES:

- 1. Withhold OR permanently discontinue pembrolizumab + epacadostat at the discretion of the Investigator.
- 2. For participants with Grade 3 or 4 immune-related endocrinopathy where withholding of pembrolizumab and epacadostat is required, pembrolizumab and epacadostat may be resumed when AE resolves to :S Grade 2 and is controlled with hormonal replacement therapy or achieved metabolic control (in case of TIDM)

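### Section 11.0 and Tables 15 and 16 set different limits on a hold for treatment-related toxicity (about 9 versus 12 weeks since the last dose), and no text says which governs

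*Combined protocol and SAP*

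**What the plan says.** Section 11.0 has two sentences on long delays. The first covers delays in general: beyond 6 weeks from the planned dose the patient may have to stop, with an exception for surgery. The second covers related toxicity and is firmer. It uses the same 6-week trigger, with no exception: if the delay is "due to the occurrence of an adverse event that is considered related to epacadostat and/or pembrolizumab, the subject should be taken off study treatment". Both sentences translate the 6 weeks into about 9 weeks since the previous dose.

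Section 11.4.1 uses a different limit.

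- Table 15 covers epacadostat-related events without immune etiology. For non-hematologic toxicity it provides for restart after resolution, at the same dose or one level lower depending on the row. Its criterion for discontinuing is "Toxicity does not resolve within 12 weeks of last dose of treatment". A footnote lets some grade 2 laboratory events continue past 12 weeks with the principal investigator's agreement.
- Table 16 covers immune-related events. General Instruction 2 lets both drugs resume once the event is grade 0 or 1 and steroids have been tapered. It says that they "should be permanently discontinued if AE does not resolve within 12 weeks of last dose", or if steroids cannot be brought down to 10 mg prednisone daily in that time. The rash and amylase/lipase rows repeat the 12 weeks.

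Section 9.1 points to Section 11.4 for dose delays due to toxicity. It does not say that Section 11.4 overrides Section 11.0, and Section 11.4 does not mention the 6-week rule.

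**The concern.** Both sets of text apply to the same patient: one whose dosing is held for a toxicity attributed to the study drugs. They give different points at which the hold ends treatment, measured from different starting points (the planned dose in one, the last dose in the other). Staff who follow Section 9.1 to Section 11.4 would not meet the shorter limit at all.

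What is at stake is whether a patient, possibly a responder, stays on the combination. Stopping also changes what is observed. After discontinuation, Section 13.0 lists a visit at about 30 days and then contacts for survival and new therapy, with no scheduled imaging. Section 12.4 requires response to be confirmed 4 weeks later. Inconsistent use of the two limits could therefore affect reported discontinuations, exposure, and the completeness of disease assessment for the few patients concerned.

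**Working it through.** **Inputs**

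- Trigger in Section 11.0: more than 6 weeks past the planned dose, "i.e., approximately 9 weeks since the previous dose) due to the occurrence of an adverse event".
- Pembrolizumab interval (Section 5.2.3): "every 3 weeks (±3 days) thereafter".
- Epacadostat interval (Section 5.1.3): "Epacadostat be taken orally twice daily on a continuous dosing schedule", doses about 12 hours apart.
- Limit in Tables 15 and 16: 12 weeks from the last dose.

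**Step 1. Reproduce the protocol's figure.** Weeks since the previous dose = dosing interval + delay. For pembrolizumab, 3 + 6 = 9 weeks, which matches the gloss. The ±3-day window moves this by at most 3/7 = 0.43 week.

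**Step 2. Put both limits on one clock (pembrolizumab).**

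| Source | Weeks past planned dose | Weeks since last dose |
|---|---|---|
| Section 11.0 | 6 | 3 + 6 = 9 |
| Tables 15 and 16 | 12 − 3 = 9 | 12 |

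The difference is 12 − 9 = 3 weeks on either clock. The passages disagree for a patient who becomes restartable more than about 9 and up to 12 weeks after the last pembrolizumab dose.

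**Step 3. Worked case.** A related toxicity that the tables allow to be held falls to grade 1, with steroids tapered, 10.5 weeks after the last pembrolizumab dose. The delay is 10.5 − 3 = 7.5 weeks. Since 7.5 exceeds 6, Section 11.0 takes the patient off treatment. Since 10.5 is less than 12, Table 16 lets both drugs resume.

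**Step 4. Check the gloss for epacadostat.** With a 12-hour interval, 6 weeks past a planned dose is 6 + 0.5/7 = 6.07 weeks since the previous dose, not 9. The gloss is therefore arithmetically right only for the 3-weekly drug. This shows that the epacadostat reference point is not defined. It does not establish a separate 6-week limit for that drug.

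**Step 5. Which events are in scope.** Where the tables already require permanent discontinuation (for example grade 3 or 4 pneumonitis, hepatic or renal events, and grade 4 colitis or rash), there is no restart to dispute. Only events that can be held and restarted are affected.

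**Step 6. Bearing on the primary test.** The exact binomial rule of 6 or more responses in 30 gives a type I error of 0.073 at a 10% response rate and power of 0.923 at 30%. This agrees with the 0.07 and 92% in Section 14.1. Neither figure depends on the length of a hold.

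**The case against.** The strongest defence is that the limits are separate stopping triggers on different quantities: Section 11.0 limits the delay, while the tables limit the time to resolution and to steroid reduction. A site could apply both and let the shorter govern. General Instruction 2 only permits resumption, so stopping at about 9 weeks breaches no prohibition in Table 16. This stands as far as it goes: a reader might infer that the two rules cannot both be obeyed, and the text does not support that. But nothing states that the shorter limit governs. That reading would also leave the 12-week limits, and the Table 15 footnote on continuing past them, with almost no effect for related events. The word *should* in Section 11.0 and the discussion with the principal investigator in Table 15 leave discretion, but they do not say which number it is exercised around.

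Two larger gaps are also tempting.

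- *Epacadostat, 6 versus 12 weeks.* A reader might infer this from Step 4. It sets aside the protocol's own 9-week gloss, and Section 11.4.1 says that when an interruption is necessary both drugs are interrupted, which favours a shared clock. Only the unclear reference point survives.
- *Time to reach grade 1, 5 versus 8 weeks.* Table 16 says that the steroid taper is to "continue to taper over at least 4 weeks". A reader might subtract 4 weeks from 9 and from 12. That assumes the whole taper must finish before restart, whereas Section 9.5 holds dosing only until the dose is down to 10 mg prednisone daily. Table 16's 12-week test is resolution and reduction to that dose, not a completed taper, and Table 15 has no taper.

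It is also fair to say that few patients may be affected; the documents give no basis for a count among the 30. Finally, Section 16.3 refers to the study as completed, so an amendment may come too late to change anyone's treatment.

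**Conclusion.** This is an internal inconsistency in the rules for stopping treatment. For related toxicities that may be held, Section 11.0 ends treatment at about 9 weeks since the last pembrolizumab dose and Tables 15 and 16 at 12 weeks, with no stated precedence. The gap of about 3 weeks rests only on the 3-week interval and the protocol's own gloss. The reference point for epacadostat is a second, smaller ambiguity.

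The finding is worth correcting but limited. It does not reach events that already require permanent discontinuation, and it leaves the sample size and decision rule as they are. Effects on exposure, discontinuation counts and disease assessment are plausible but not quantified. No view is taken on which limit is clinically right.

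**What to change.** Reconcile Section 11.0 with Tables 15 and 16, including the Table 15 laboratory footnote and the rash and amylase/lipase rows. One maximum delay for related toxicity should apply throughout, with a stated reference point (planned dose or last dose) for each drug. The clinical team must choose the limit. If two criteria are meant to coexist, one for length of delay and one for time to resolution, say so and say which takes precedence.

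The cost is a wording change in one amendment, with no added procedures or patients. If treatment has ended, record instead which limit was applied and, when reporting discontinuations, identify any patient whose hold fell between about 9 and 12 weeks. That needs only the dosing records.
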